9.2.3 Subject Selection Criteria

Subjects must be prescribed Obizur for the treatment of a bleeding episode by a physician, prior to the decision to enroll in the study.

9.2.3.1 Inclusion Criteria

Subjects who meet ALL of the following criteria are eligible for this study:

- 1. Subject is ≥ 18 years of age at the time of informed consent.
- 2. Subject has AHA, and is being treated/was treated with Obizur.
- 3. Subject is willing and able to comply with the requirements of the protocol.

9.2.3.2 Exclusion Criteria

Subjects who meet **ANY** of the following criteria are not eligible for this study:

- 1. Subject has a known anaphylactic reaction to the active substance, to any of the excipients, or to hamster protein.
- 2. Subject has a concomitant bleeding disorder(s) other than AHA.
- 3. Subject has participated in another clinical study involving a medicinal product or device within 30 days prior to enrollment or is scheduled to participate in another clinical study involving a medicinal product or device during the course of the study.

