9. RESEARCH METHODS

9.1 Study Design

This study is a multi-center, uncontrolled, open-label, non-interventional postauthorization safety surveillance study to describe the use of Obizur in patients with AHA, and secondarily, where data are available, to describe the hemostatic effectiveness and immunogenicity of Obizur. Approximately 40 male and female patients ≥18 years of age with AHA in the United States will be enrolled over a 3.5 year period with follow-up from the date of treatment through 180 days; it is expected this prospective study will enroll up to two patients per month. Patients should be enrolled within five days of initiating Obizur to ensure unbiased prospective observation.

In addition, in an attempt to collect all safety and utilization data on patients treated with Obizur since Food and Drug Administration approval in October 2014, Baxalta will conduct a retrospective chart review on persons treated with Obizur prior to the prospective study start date. Baxalta expects there will be approximately 30 to 40 patients who were treated with Obizur prior to the study start date, on whom retrospective data will be collected.

Prospective data will be collected for each subject over a period of approximately 180 days from the time of Obizur treatment; in addition, data points that are retrospective in nature (such as comorbidities and prior medical treatment) will be obtained from the medical chart for the time period prior to Obizur treatment. A subject or a subject's legally authorized representative will provide signed informed consent according to local regulations, prior to data collection initiation. Signed informed consent should be obtained within five days of Obizur treatment for patients newly treated with Obizur.

Among patients in the retrospective cohort, for whom Obizur treatment occurred prior to initiation of the prospective study, signed informed consent will be obtained at the time the patient has a clinic visit. If the patient is deceased or lost to follow-up, only anonymized data will be collected from the medical chart and entered into the electronic data capture (EDC) system.

The choice of Obizur use is to be made *independent of and prior to* any decision by the subject or the subject's legally authorized representative to participate in this study. The treating physician will determine the treatment regimen, as well as frequency of laboratory and clinical assessments, according to routine clinical practice.

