9.2.6 Screening and Follow-up

The study site is responsible for maintaining an enrollment/screening log that includes all subjects enrolled. The log also will serve to document the reason for screening failure or decision to not enroll. All screening data will be collected and reported in CRFs, regardless of screening outcome. If a subject is re-screened, the End of Study CRF should be completed, and a new ICF, new SIC and new CRF are required for that subject.

The overall study design is illustrated in Figure 1.

Figure 1
Study Design for Baxalta Non-Interventional Study Protocol 241302

Obizur [antihemophilic factor (recombinant), porcine sequence]
prescribed by a physician

ective data collection if treatment prior to study initiation (with ontion

- Retrospective data collection if treatment prior to study initiation (with option for follow-up duration: 180 days post-treatment); enroll at first clinic visit
- Prospective data collection (duration: 180 days) if treatment on or after study initiation; up to five days to enroll from treatment initiation

[figure not shown]

Table 1. **Schedule of Study Assessments**

		Baseline	Interval/Data available per existing patient visits, medical charts						Study
Assessments	Screening		Time A	Time B	Time C	Time D	Time E	Time F, etc.	Completion/ Termination ^a
Informed Consent b	X					0			
Eligibility Criteria ^b	X				C				
Demographic Information		X							
AHA Information		X	X	X	X	X	X	X	
Medical History		X	X	X,C	X	X	X	X	
Concomitant Medications		X	X	X	X	X	X	X	X
Safety: SAEs		X	X	X	X	X	X	X	X
Laboratories (as available) c		X	X	X	X	X	X	X	X
Obizur Treatment Information		X	CX	X	X	X	X	X	X
Concurrent Bleeding Episodes		X	X ^d	X^{d}	X^d	X^d	X ^d	X^{d}	

- a Include for cases of withdrawal or discontinuation.
 b Occurs before start of data collection.
 c For laboratory assessments, see Table 2.
 d Only if additional bleeds occur.

Table 2. Clinical Laboratory Data Collection Clinical Laboratory Data Collection									
	c ·	D II	Interv	al/Data ava	Study				
Assessments	Screening	Baseline	Time A	Time B	Time C	Time D	Time E	Time F, etc.	Completion/Terminationa
Hematology*								11	
Hemoglobin		X							
Hematocrit		X							
CBC with differential, if consistent with local practice		X							
FVIII anti-human and anti-porcine antibodies±		X							

^{*}Given the observational nature of this study, data will be collected as recorded. No laboratory assessments are mandated by this Protocol.

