9.3.5 Safety (collect all SAEs; endpoint is therapy-related SAEs)

For the purpose of this study only serious adverse events (SAEs) will be collected. Reasons for collecting SAEs only include the following: Patients enrolled in this study are often elderly with a multitude of comorbidities and high medication intake. Additionally, they are seriously diseased receiving treatment in intensive care units. Thus, making qualified assessments of non-serious AEs with respect to isolated medicinal products is next to impossible given the multitude of treatments administered concomitantly.

- Key safety concerns:
 - > Inhibitor development against pFVIII (post baseline)
 - Date of inhibitor draw
 - > Hypersensitivity reactions including anaphylaxis
 - > Thrombogenicity
 - > Outcomes, including death (yes/no, date of death)

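### Exclusion criterion 1 has no time reference and is applied after Obizur exposure, so read literally it removes patients whose anaphylaxis to the index course came before the eligibility check

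*Protocol*

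**What the plan says.** Exclusion criterion 1 (Protocol, Section 9.2.3.2) reads: "Subject has a known anaphylactic reaction to the active substance, to any of the excipients, or to hamster protein". It gives no date or reference point. Inclusion criterion 2 (Section 9.2.3.1) reads: "Subject has AHA, and is being treated/was treated with Obizur". Exposure is therefore a condition of entry.

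Timing of enrollment:
- **Prospective cohort.** Section 9.1 says "Patients should be enrolled within five days of initiating Obizur to ensure unbiased prospective observation" and "Signed informed consent should be obtained within five days of Obizur treatment for patients newly treated with Obizur". Figure 1 in Section 9.2.6 repeats this: "Prospective data collection (duration: 180 days) if treatment on or after study initiation; up to five days to enroll from treatment initiation".
- **Retrospective cohort.** Section 9.1 says "signed informed consent will be obtained at the time the patient has a clinic visit", which is after treatment has taken place.
- **Eligibility check.** Table 1 puts it at screening, before data collection begins.

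What is to be counted:
- Section 8.2 makes the incidence of therapy-related SAEs the primary objective.
- Section 9.3.5 lists among the key safety concerns "Hypersensitivity reactions including anaphylaxis".
- Section 9.1.2 makes hypersensitivity reactions a secondary outcome.
- Section 11.1.2 starts SAE recording at Obizur treatment, not at consent.
- Section 9.1 says that the retrospective review is done "in an attempt to collect all safety and utilization data on patients treated with Obizur since Food and Drug Administration approval in October 2014".

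**The concern.** In a trial that screens before dosing, a known reaction to the product is a baseline characteristic. Here screening follows exposure, so a reaction to the index course can already be known when the criteria are applied. The same event is then both an outcome and a reason not to enroll the patient who had it. That is selection on the outcome, and it acts in one direction only: a patient who reacted is removed, and a patient who did not react stays.

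The retrospective cohort is the more exposed of the two, because its eligibility check comes after treatment has taken place. In the prospective cohort the exposed interval is at most five days, but it includes the first infusions whenever consent follows them. Section 9.1 justifies the five-day window as protecting unbiased observation, and an outcome-dependent exclusion inside that window works against this purpose. An analysis plan cannot recover patients who were never enrolled.

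**Working it through.** **1. Does the text exclude an index-course reaction?**
- Section 9.2.3 requires that Obizur be prescribed before the decision to enroll, and inclusion 2 requires that treatment is under way or past.
- Exclusion 1 has no time anchor. Other criteria do: inclusion 1 fixes age at consent, and exclusion 3 uses 30 days before enrollment. Nothing in the wording of exclusion 1 tells a site to read it as history before the first infusion.
- Section 11.1.2 counts SAEs from Obizur treatment. An anaphylactic SAE between first infusion and the eligibility check is therefore countable under Section 11.1.2 and disqualifying under Section 9.2.3.2.

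**2. Does other text repair this?**
- Section 9.7.1 puts all treated subjects in the analysis dataset. It does not say that ineligible patients are analyzed; read that way, it contradicts Section 9.2.3.2.
- Section 9.2.6 keeps screening data and reasons for screen failure. It does not put a screen failure into the numerator or denominator.
- Sections 9.1 and 9.2.4 allow anonymized chart data for deceased or lost patients. They do not address exclusion 1, and they do not cover patients who are alive and in contact.
- Section 10.4 asks for no selectivity, but within the eligibility criteria, so it does not set exclusion 1 aside.

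**3. The plan's own interval.** Section 9.5 uses the exact Clopper-Pearson method. With x events in n patients, the lower limit is the 0.025 quantile of Beta(x, n − x + 1) and the upper limit is the 0.975 quantile of Beta(x + 1, n − x). For 5% of 40, x = 2, which gives 0.61% to 16.92%. This reproduces the stated 0.6% to 16.9%.

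**4. Illustration on the planning case.** Section 9.2.8 ends enrollment once at least 40 prospective subjects are in, so an excluded patient is assumed to be replaced by one without an event and n stays at 40.

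| Patients with a related SAE who are excluded | Result | Exact 95% CI |
|---|---|---|
| None | 2/40 = 5.0% | 0.6% to 16.9% |
| One | 1/40 = 2.5% | 0.1% to 13.2% |
| Both | 0/40 = 0% | 0% to 8.8% |

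**5. Range in expectation.** Let p be the true proportion with a related SAE, and f the share of those patients removed because of anaphylaxis before the check. The proportion among patients who remain eligible is q = p(1 − f) / (1 − pf). The protocol does not give f, so the values below are assumptions. For example, p = 5% and f = 50% gives 0.025 / 0.975 = 2.6%.

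| f | q if p = 5% | q if p = 10% |
|---|---|---|
| 10% | 4.5% | 9.1% |
| 25% | 3.8% | 7.7% |
| 50% | 2.6% | 5.3% |
| 100% | 0% | 0% |

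For any f above zero, q is below p.

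**The case against.** The best counter-argument is that criterion 1 is an ordinary allergy-history criterion. It names excipients and hamster protein alongside the active substance, which suggests prior sensitivities. An investigator who reads the whole protocol, with its instruction to record SAEs from treatment and its naming of anaphylaxis as a safety concern, might well report an index reaction as an SAE and enroll the patient. This may be what was intended, and it limits the charge: the wording can be misapplied, and nothing shows that every site would do so. It does not remove the problem, because the text does not state that intention and the sections conflict when each is followed as written.

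Three further points stand. Five days is a maximum, so same-day consent is possible and the number of reactions that precede it is unknown. The screening log would make such exclusions visible. The anonymized-data route might admit a fatal case, since inclusion criteria 1 and 3 cannot be applied literally to deceased patients.

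A reader might also infer that no anaphylaxis to Obizur could ever be counted in the retrospective cohort. The protocol does not support that. Section 9.2.2 provides some prospective data collection for several of these patients, up to 180 days after treatment, and allows retreatment for later bleeds with follow-up restarting. A reaction after the eligibility check can be counted in either cohort.

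**Conclusion.** The point holds as a conflict between the eligibility rule and the safety outcomes. Criterion 1, read literally, excludes patients with anaphylaxis to the index course before eligibility is checked, while Sections 8.2, 9.1.2, 9.3.5 and 11.1.2 call for that event to be counted. The resulting bias in the incidence of therapy-related SAEs and of hypersensitivity is downward.

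A reader might infer that the rule removes the study's safety events in general. It does not: thrombotic events, inhibitor development, other related SAEs and reactions after the check are untouched.

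The size is unknown, because no anaphylaxis rate is given. The fall from 5.0% to 2.5% with one excluded patient shows how sensitive a proportion based on about two expected events is; it is not a forecast. It assumes the 5% planning value, replacement of the excluded patient by one without an event, and sites that apply the criterion as written.

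**What to change.** Limit criterion 1, for both cohorts, to reactions documented before the first infusion of the index Obizur course. Add that a reaction during or after the index course is an outcome and not a reason for exclusion from the study. Review the screening log for treated patients who were not enrolled under criterion 1, and report their number and the reason.

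The cost is a short protocol amendment and a check of a log that sites already keep. No extra patients, visits or tests are needed. The change concerns study eligibility wording only and does not touch treatment.

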9.2.4 Informed Consent and Enrollment

Any patient who provides informed consent (i.e., signs and dates the informed consent form and assent form, if applicable) is considered enrolled in the study. A legally authorized surrogate may also sign the informed consent. If the patient is deceased or lost to follow-up, only anonymized data will be collected from the medical chart and entered into the electronic data capture (EDC) system.

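### For retrospective patients, exclusion 3 counts its 30 days back from consent rather than from Obizur treatment, so it usually checks a period after the exposure and cannot be applied to deceased or lost patients

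*Protocol*

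**What the plan says.** Exclusion 3 (Section 9.2.3.2) has two limbs. The first looks back: "Subject has participated in another clinical study involving a medicinal product or device within 30 days prior to enrollment". The second looks forward: the subject "is scheduled to participate in another clinical study involving a medicinal product or device during the course of the study".

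Section 9.2.4 fixes the anchor of the first limb: "Any patient who provides informed consent" "is considered enrolled in the study".

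The criteria are written once, for both cohorts. Inclusion 2 (Section 9.2.3.1) reads "Subject has AHA, and is being treated/was treated with Obizur". No separate version of exclusion 3 is given for patients treated before the study opened.

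The cohorts reach consent differently. Section 9.1 asks that prospective patients be enrolled within five days of starting Obizur. For the retrospective cohort it says that "signed informed consent will be obtained at the time the patient has a clinic visit", and Figure 1 (Section 9.2.6) says "enroll at first clinic visit". Neither place limits the gap between treatment and that visit. Patients who have died or been lost contribute anonymised chart data only (Sections 9.1 and 9.2.4).

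The retrospective review is done "in an attempt to collect all safety and utilization data on patients treated with Obizur since Food and Drug Administration approval", which Section 9.1 dates to October 2014.

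**The concern.** An other-study exclusion in a single-arm safety study is normally there to keep a second study product from clouding whether a serious event was related to the drug of interest. The protocol states no purpose for exclusion 3, so this is an inference, but it fits a primary objective built on therapy-related SAEs. To do that job the window has to sit around the exposure. In the retrospective cohort it sits around a consent visit that may come most of a year later.

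Two errors could follow: removing patients because of something that happened after their exposure, and retaining patients whose exposure overlapped another study. A rule that depends on consent can also act only on patients who are available to give it. Retrospective subjects enter the annual reports (Section 9.2.2), and Section 9.5 allows for some to be assessed with the prospective cohort, taking the total from 40 to 50. At 50, one subject is 1/50 = 2 percentage points of the incidence proportion.

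**Working it through.** The protocol gives no figure on this point. Its only size figures, the exact intervals in Section 9.5, reproduce at a 5% event proportion (0.61% to 16.92% for 40 subjects, 0.84% to 15.15% for 50), but nothing below depends on them.

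**Inputs**
- Look-back: 30 days, ending at enrolment (Section 9.2.3.2).
- Enrolment: date of consent (Section 9.2.4).
- Retrospective treatment dates: October 2014 (Section 9.1) to the day before study start, planned for 30 September 2015 (Section 6).
- Follow-up: 180 days after treatment (Section 9.2.2).
- Retrospective cohort: about 30 to 40 patients (Section 9.1).
- Consent dates tried: 30 September 2015 (the earliest), and 15 December 2015 (the data lock for the retrospective report in Section 6, used as a later example).

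**Formula.** Let g be the days from treatment to consent. Counted from treatment, the look-back covers day g − 30 to day g. A window that checks for other studies before exposure would cover day −30 to day 0.
- The look-back lies wholly after treatment began when g > 30.
- It lies wholly after the 180 days when g − 30 > 180, that is, g > 210.

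**Prospective patients.** With g between 0 and 5, the look-back starts at day −30 to −25 and ends at day 0 to +5. It is in the right place.

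**Retrospective patients**

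| Treated | 180 days end | Look-back if consent 30 Sep 2015 | Look-back if consent 15 Dec 2015 |
|---|---|---|---|
| 31 Oct 2014 | 29 Apr 2015 | day +304 to +334 | day +380 to +410 |
| 1 Jan 2015 | 30 Jun 2015 | day +242 to +272 | day +318 to +348 |
| 1 Apr 2015 | 28 Sep 2015 | day +152 to +182 | day +228 to +258 |
| 1 Jul 2015 | 28 Dec 2015 | day +61 to +91 | day +137 to +167 |
| 1 Sep 2015 | 28 Feb 2016 | day −1 to +29 | day +75 to +105 |
| 29 Sep 2015 | 27 Mar 2016 | day −29 to +1 | day +47 to +77 |

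**Cut-offs for consent on 30 September 2015**
- 30 Sep 2015 − 30 days = 31 Aug 2015. Anyone treated before then has a look-back wholly after treatment began.
- 30 Sep 2015 − 210 days = 4 Mar 2015. Anyone treated before then has a look-back wholly after the 180 days.

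Later consent moves both dates later. At 15 December 2015 they are 15 November 2015, which takes in every retrospective patient, and 19 May 2015.

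**Share of the cohort.** This needs an assumption that is not in the protocol: treatment dates spread evenly from October 2014 to study start, all consenting on 30 September 2015. The span is 334 days from 31 October or 364 days from 1 October.
- Look-back wholly after treatment began: 304/334 = 91% to 334/364 = 92%, or about 27 of 30 to 37 of 40.
- Look-back wholly after the 180 days: 124/334 = 37% to 154/364 = 42%, or about 11 of 30 to 17 of 40.

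These count patients whose window is misplaced, not patients wrongly excluded or kept.

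**What the text then does**
1. A patient treated on 1 January 2015 completes the 180 days on 30 June, joins another drug study in mid-September and consents on 30 September. Exclusion 3 removes that patient, although the exposure and follow-up were free of the other study.
2. A patient treated on the same day while in another drug study that ended in February 2015 consents on 30 September. The look-back starts on 31 August, so the patient stays eligible. The forward limb concerns planned participation and cannot reach a past study.
3. A deceased or lost patient has no consent date. g is undefined and the look-back cannot be applied.

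**The case against.** Several points on the other side are sound.

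- **The main cohort is unaffected.** The 40 prospective patients on whom the study size rests are screened in the right place. Retrospective data join them only conditionally (Section 9.5), on terms left to the SAP (Section 9.2.2). This limits the reach of the point but does not repair the rule.
- **The look-back is not irrelevant for every retrospective patient.** Some are still inside their 180 days at consent, and Section 9.2.2 expects part of their data to be collected prospectively. For patients treated roughly from March to August 2015 the look-back can fall inside the 180 days, and an exclusion there is not clearly the loss of a valid exposure.
- **Confounding is partly controlled elsewhere.** Section 9.3.7 records all medications from 14 days before product administration, and Section 11.1.2.2 has the investigator weigh concurrent treatments. These may reveal a study product, but they leave eligibility unchanged and do not reach days −30 to −15.
- **The forward limb may be harmless.** A reader might infer that it covers the whole four-year study. Sections 9.3.11 and 11.1.2 also use study completion for the individual subject, so it can be read as the subject's own follow-up. The text does not say which is meant. That calls for a clarification and is not a demonstrated fault.
- **Excluded patients' SAEs may not vanish.** Section 9.2.6 keeps screening data whatever the outcome, and Section 9.7.1 puts all treated subjects in the analysis dataset. Neither settles whether an ineligible patient's events are analysed, so certain loss cannot be claimed.

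**Conclusion.** The point holds for the retrospective cohort only. Read as written, exclusion 3 generally looks at a period after Obizur was started. For patients treated before about 4 March 2015 and consenting on 30 September 2015, it looks only at a period after the 180 days. It can exclude on later participation, it can miss participation concurrent with Obizur, and it acts only on patients available to consent. No other section corrects this. The cut-off dates rest on the planned start date, and the cohort shares rest on evenly spread treatment dates.

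The effect is structural, and its size is unknown. The protocol gives no rate of participation in other studies, and the number affected is probably small. A reader might assume a rate, say 5% to 10%, and multiply by 30 to 40 to get 1.5 to 4 patients lost. That is not supported: the rate has no source in the protocol, and the base includes deceased and lost patients, whom the rule cannot exclude. A reader might also infer a survival bias in the SAE incidence. The rule does act only on those who can consent, but data on the deceased are deliberately kept, and nothing in the protocol gives a direction or size. Nor is the aim of collecting all data since approval flatly contradicted, because it is worded as an attempt. The exclusion works against that aim without need.

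**What to change.** In Section 9.2.3.2, add a version of exclusion 3 for the retrospective cohort, expressly including deceased and lost patients:

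- Count participation in another medicinal product or device study within the 30 days before the first Obizur infusion of the qualifying bleed.
- Do not exclude for participation that began after that bleed's 180-day period.
- Record by date any investigational product used within the 180 days, so that relatedness of SAEs can be judged against it.

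For prospective patients, leave the look-back and the concurrent-study limb as they are. Add only that 'course of the study' means the subject's own follow-up.

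The cost is a few lines of text and a small chart check. The medication record in Section 9.3.7 starts 14 days before administration, so participation in days −30 to −15 has to be looked up separately. No visit, test or sample-size change is needed.
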